### **Data Management Procedures and Confidentiality:**

All data will be entered into the electronic database REDCap via a secure WUSM web portal and stored on secure WUSM servers, which can be accessed securely through the WU or FAU networks. The database management is built with multiple layers of security and follows best practices and WUSM requirements for securing sensitive data. The iOTA program will be monitored through a secure web-portal via the WU network. All automatic system generated messages in the iOTA program will be sent directly to subjects' mobile phones

through an online application developed and supported by technology vendor, Integrity, who has existing WU IRB and Information Security office approval for involvement with the parent iOTA program. The research team will use the iOTA online web portal from WU computers on the WU network. Integrity captures/stores all text messaging data (data sent to participants and received back from participants) and transmits the data to the WU research team using the REDCap API via a secure WUSM web portal stored on secure WUSM servers.

### **Data Analysis/ Statistical Considerations:**

Planned primary and secondary analysis: In addition to the use of change in body weight from baseline as the primary outcome for this pilot study, secondary outcomes will include change in BMI, psychophysical skills and related self-efficacy. Weight/BMI will be measured at each visit (up to 10 visits over 9 months); we will use a repeated-measures mixed model to look at trajectory over study course with a time x treatment interaction estimating the treatment effect. Increase in self-efficacy for diet and exercise is the proposed mechanism of action for the active iOTA intervention. Measures of Psychophysical Awareness will be measured at every visit (total of 5 time points). Trajectory of self-efficacy scores will be compared between treatment groups. Finally, we will use structural equation growth models to estimate the correlation between the trajectory of psychophysical skills and related self-efficacy and that of weight/BMI.

Exploratory analyses: will focus on characterizing feasibility, engagement and implementation challenges as measured by i) enrollment, retention and visit adherence, ii) obesity intervention acceptability, iii) text response rates, iv) client expectations, v) fidelity and vi) client and staff-rated feasibility, appropriateness, acceptability, and vii) staff burden, including evaluation of how these variables impact effectiveness with respect to BMI and self-efficacy. Exploratory analyses will also evaluate how mental health self-efficacy and psychotropic medication compliance impact iOTA treatment compliance/engagement.

### **Safety and Adverse Events:**

#### **Safety and Compliance Monitoring**

- The Principal Investigator at each site will provide overall monitoring of the data collection, and data safety throughout the study process. The Project Coordinator will also assist in the monitoring and supervision of data collection and will report any concerns to the PI at their site. All PI's and Project coordinators will attend monthly meetings where any concerns regarding subject safety or data security will be communicated promptly to the 3 lead sites and handled accordingly.
- University and NICHD guidelines will be followed for reporting should an adverse event occur. Monitoring will include checking to see that data files are appropriately stored and bi-weekly group supervision of field interview staff to discuss the process, answer questions and provide assistance when needed. The project will also undergo review and approval by our Institutional Review Board with monitoring as required by annual reports and recertification of human subjects approval. The Data Safety Monitoring Board will meet at least annually and sooner if any needs arise to consult regarding any concerns about the ongoing safety and well-being of participants. These members are expertise in areas of administrative data and child welfare reporting, both key issues pertinent to study implementation.

#### **Medical Monitoring**

- Independent Data and Safety Monitoring Board – The Principal Investigator will provide overall monitoring of the data collection, participants, and data safety throughout the study process. Washington University and NICHD guidelines will be followed for reporting should an adverse event occur. Monitoring will include checking to see that data files are appropriately stored and regular supervision of study staff involved in data collection to discuss the process, answer questions and provide assistance when needed. The project will also undergo review and approval by our Institutional Review Board with monitoring as required by annual reports and recertification of human subjects approval. The Investigators will meet monthly, and should any concerns arise regarding the ongoing safety and well-being of participants they will be addressed accordingly. Additional oversight will be provided by the National Center for Translational Science program officer who attends the monthly PI meetings.

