## **Expectedness**

- AEs that are unanticipated will be reported immediately to the Washington University in St. Louis IRB by the PI. The IRB will determine whether it is appropriate to stop the study protocol temporarily or will provide suggestions/modifications to the study procedures. Possible modifications include adding these possible adverse events to the consent form and re-consenting all study participants. The PI will be responsible for monitoring participant safety on a monthly basis at regularly scheduled research meetings. The PI will keep a written log of all adverse events and ensure that the IRB is contacted immediately. The PI will also keep a log of the outcome of IRB decisions regarding adverse events and enforce any changes that need to occur as a result of the IRB decisions. If the preliminary outcome data indicates harmful impact of the program to caregivers or their families, the Washington University in St. Louis committee will be notified and it is possible that the study will be discontinued.

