## **Data Collection Procedures for Adverse Events**

- The PI will be responsible for monitoring participant safety on a monthly basis at regularly scheduled research meetings. The PI will keep a written log of all adverse events and ensure that the IRB is contacted immediately and will also keep a log of the outcome of IRB decisions regarding adverse events and enforce any changes that need to occur as a result of the IRB decisions. If the preliminary outcome data indicates harmful impact of the program to caregivers or their families, the Washington University in St. Louis committee will be notified and it is possible that the study will be discontinued.

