## **Reporting Procedures**

- The PI will be responsible for monitoring participant safety on a weekly basis. He will be informed of any adverse events (AE) as soon as they occur, and he will report them to the Washington University in St. Louis IRB within 24 hours of becoming aware of the event. The IRB will determine whether it is appropriate to stop the study protocol temporarily or will provide suggestions/modifications to the study procedures. Possible modifications include adding these possible adverse events to the consent form and re-consenting all study participants. Because this study takes place at 13 sites, the PI will also be responsible for notifying all other site's PI's.
- Additionally, in accordance with NIH policy, the PI will notify the study's NIH program officer within 10 business days of the study team becoming aware of an unexpected serious adverse event (SAE). For all AEs or serious adverse events (SAE) that are either expected or unrelated to the study, the PI will provide a summary to the study's NICHD program officer with the annual progress report.

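### The safety-oversight text contradicts itself on who the independent board is, and its only outcome-data trigger names caregivers and families, not the 60 randomised participants

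*Protocol*

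**What the plan says.** **Who monitors.** In the protocol's Medical Monitoring section the single bullet begins "Independent Data and Safety Monitoring Board – The Principal Investigator will provide overall monitoring of the data collection, participants, and data safety throughout" the study. It goes on to staff supervision, IRB review, an investigators' meeting ("The Investigators will meet monthly, and should any concerns arise regarding the ongoing safety and well-being of participants they will be addressed accordingly") and a funder representative ("Additional oversight will be provided by the National Center for Translational Science program officer who attends the monthly PI meetings"). No board members, remit or charter follow.

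The preceding section, Safety and Compliance Monitoring, names a board: "The Data Safety Monitoring Board will meet at least annually and sooner if any needs arise". Its purpose is "to consult regarding any concerns about the ongoing safety and well-being of participants". Its members' expertise is given as administrative data and the reporting of child welfare matters. The section does not say that the board is independent of the investigators, what data it receives, or whether it can pause the study.

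**What triggers discontinuation.** Expectedness, repeated in Data Collection Procedures for Adverse Events, contains the only rule tied to outcome data: "If the preliminary outcome data indicates harmful impact of the program to caregivers or their families", a university committee is told and the study may be discontinued. No threshold, analyst or schedule is given.

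**How often the PI looks.** Data Collection Procedures for Adverse Events says "The PI will be responsible for monitoring participant safety on a monthly basis at regularly scheduled research meetings", and Expectedness agrees. Reporting Procedures says "The PI will be responsible for monitoring participant safety on a weekly basis".

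**What goes to the IRB.** Expectedness opens with unanticipated adverse events. Reporting Procedures has the PI report any adverse event within 24 hours, after which the IRB may halt the protocol temporarily. The SAP does not mention safety data or their review.

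**The concern.** A reader trying to follow these sections cannot tell which body is independent of the investigators. The bullet that carries the word describes the investigators themselves, and the board named elsewhere is not called independent. The rule meant to stop the study on outcome data names people whose outcomes Aim 3 does not measure and omits those whose outcomes it does.

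This matters most for harm that builds up slowly. The trial is open-label, and the PIs review the recorded coaching sessions. Depressive symptoms (PHQ-9) and clinical global impression are recorded at each visit. The stated response to a PHQ-9 score above 10 is a choice of coaching content, and no section sends the score to safety review. A drift in one arm need not become a reported adverse event, and an as-needed board meeting depends on someone noticing the drift. No one is assigned to tabulate harms by arm.

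**Working it through.** The plan gives no error rate, power or stopping boundary here, so the check is a comparison of sections.

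1. **Board.** Medical Monitoring uses the label of an independent board and describes the PI, the investigators, the IRB and a program officer. Safety and Compliance Monitoring describes a board without calling it independent. Read together, no body is both a board and stated to be independent of the investigators.

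2. **Expertise.** Aim 3 (Study Participants) enrols adults aged 18-45 with serious mental illness in a weight intervention. The stated expertise of the board covers neither psychiatry nor weight management.

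3. **Trigger against data.** The protocol's assessment sections were read in turn: baseline only; baseline and endpoint; the participant's digital battery; the health coach's forms; the midpoint and endpoint questionnaires. Respondents are participants, health coaches and case managers or community support workers. The number of assessments measuring a caregiver or family health outcome is 0. The number of randomised participants whom the trigger names is 0 of 60. On Aim 3 data the trigger therefore has nothing to act on.

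4. **PI review interval.** Monthly in Expectedness and in Data Collection Procedures for Adverse Events; weekly in Reporting Procedures.

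5. **IRB reporting scope.** Expectedness starts from unanticipated events, though its later sentence on a log of all events could be read more widely. Reporting Procedures covers any event. Adverse Event Reporting Period repeats the 24-hour limit without restricting the type of event.

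6. **What does cover participants.** The board in Safety and Compliance Monitoring has participants' well-being as its remit and can meet early. The IRB receives adverse events within 24 hours and can pause the study. Investigators may withdraw a participant for safety (Participant Withdrawal). None of these is a scheduled review of accumulated data by arm.

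**The case against.** The strongest reply is that participants are protected in practice, and much of it stands. The named board is charged with their well-being and need not wait a year. Reporting Procedures sends any adverse event to the IRB within 24 hours, with power to pause. A funder's officer sits in on the monthly PI meetings. Weekly PI review would also satisfy a monthly requirement, so that discrepancy is minor. Caregivers do take part in Aim 1 and briefly receive the text messages, so naming them in a harm rule is not absurd. By-arm tables in a 60-person behavioural pilot are partly a matter of preference, and no document requires them.

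Three stronger readings are tempting and are not supported:

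- **That participant harm has no independent reviewer and no trigger.** The IRB route and the as-needed board contradict this.
- **That a pattern of harm could not reach anyone able to pause the study.** Events reported as adverse events, including a hospitalisation so reported, reach the IRB. The gap concerns cumulative change that is never reported as an event.
- **That a calculable share of participants goes unreviewed.** Randomised follow-up is 24 + 12 = 36 weeks, and yearly meetings may be about 52 weeks apart, so someone could start and finish between two meetings (52 − 36 = 16 weeks to spare). Turning that into a proportion needs an enrolment pattern that the documents do not give, and assumes no early meeting. It would not measure undetected harm either, because the board could still see those data at its next meeting.

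The reply leaves the label and the trigger untouched: both are wrong as written.

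**Conclusion.** The point holds in a limited form. The oversight sections contradict one another on the identity of the independent board, the PI's review interval and the scope of IRB reporting. The only outcome-data trigger names people with no Aim 3 outcomes and omits all 60 randomised participants. Two elements are absent: a scheduled independent review of cumulative participant harm, and an outcome-data trigger that applies to participants. Event-level review is in place.

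The size cannot be put as a probability. The conclusion rests on the text alone and assumes that no separate board charter fills the gap. References elsewhere in the safety and risk sections to child subjects, gene variants, genetic data and 13 sites suggest wording carried over from another study. That is an inference, and the finding does not depend on it. The trial is a small behavioural pilot, but its participants are vulnerable and the correction is cheap, so it should be made.

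**What to change.** - **Board.** Reconcile Safety and Compliance Monitoring with Medical Monitoring so that one board is identified, stated to be independent of the investigators, and given expertise suited to adults with serious mental illness. Label the Medical Monitoring bullet as PI oversight. Simply declaring the existing board independent would not be enough, given its unstated status and mismatched expertise.
- **Trigger.** Correct Expectedness and Data Collection Procedures for Adverse Events so that the rule covers the randomised participants, and say which committee is notified. The sponsor and board should set any pausing criteria.
- **Consistency.** Reconcile the PI review interval and the adverse-event reporting scope across Expectedness, Data Collection Procedures for Adverse Events, Reporting Procedures and Adverse Event Reporting Period. Check the rest of the safety text for wording that does not belong to this trial.
- **Review.** Give the board a cumulative summary by arm at each scheduled meeting: adverse-event log, PHQ-9, CGI and withdrawals.

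The cost is protocol rewording and one summary table per meeting. Visit data are already in REDCap. The adverse events are in the PI's written log and would need transcribing. If the present board lacks the right expertise, changing its membership adds some effort.

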## **Definitions of Adverse Events**

The most serious risk in the proposed research is any adverse outcome that may jeopardize the welfare of participants or caregivers. Possible adverse events that are anticipated include an unintentional disclosure of personal health information to an unauthorized individual. Additionally, it is possible that during the tele-health mediated assessment phase of this project, the individual or their caregiver could conceivably experience an acute medical event requiring immediate medical attention. In the unlikely event that this were to occur, the study staff would assist the participant or their caregiver in alerting local EMS, or alternatively would contact local EMS on their behalf.

## **Relationship**

- Parents or caregivers of participants must have permanent custody (i.e., not a foster parent) and will be excluded if they have severe mental health disorders (e.g., psychotic disorders) or severe cognitive delay that diminishes their capacity to consent or effectively participate in the study.
- Child subjects will include only those with a variant in a suspected brain gene. Should there be more than two children in the family with the same genetic variant will enroll them as individual participants.
- Special classes of subjects: The participants may be considered vulnerable due to developmental delays, intellectual disability or other medical conditions caused by their genetic variant. It is impossible to assess the outcomes of the study without their inclusion. Several aspects of the study reduce concerns in this area: (1) we are drawing from a population receiving services as usual from Intellectual Disabilities Research Centers with expert clinicians doing the initial screening and judgment about inclusion and exclusion, (2) the team has extensive research and clinical experience with children and families impacted by developmental delays and other genetic disorders, (3) the study procedures are brief and designed to take place within a typical clinic visit, and are designed to be implemented in a fully remote format.

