**Exclusion criteria:** i) not willing/able to provide written informed consent; ii) participants under age 18.

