**Table 1: Focus Group Makeup and Questions**

Focus Group	# Groups per Site	Participants	Areas of Interest
CMHC Administrators	1	Medical Director (1), Director of Nursing (1), Clinical Director (1), Case Manager Supervisor (1), Clinic Manager (1)	1) What should the qualifications and characteristics of the health coach be? Is it reasonable for the health coach to be an existing CMHC clinical or other type of staff member? Or should it be someone else? 2) How often should health coaches meet with clients face-to-face? What should the content of the meetings be? 3) How frequent should text messages be? What should the content of the messages be? Is it helpful to have two-way texting capability?
CMHC Prescribers	1	Psychiatrists (1-2), Advanced Practice Nurses (1), Physician Assistants (1), Primary Care Physicians (1)	4) How much time could an existing staff member devote to intervention delivery? What would the optimal amount of time be for intervention effectiveness?
CMHC Case Managers	1	Case Managers (2) and Community Support Workers (2-3) from adolescent and adult teams	5) Are there age-specific modifications needed to make the intervention more feasible/acceptable to adolescents and young adults? 6) Are there modifications needed to address other social determinants of clients and caregivers? (Race/ethnicity, gender, socio-economic status, level of education?)
CMHC Nursing Staff	1	Nursing staff (1-2), nurse care managers (1-2), nurse health coaches (1)	
CMHC Clients	2 - Group composition will reflect the racial and ethnic distribution of the population at each site.	Adult clients ages 18-45 (2-3)	
CMHC Client Family/Caregivers	2 - Group composition will reflect the racial and ethnic distribution of the population at each site.	Parents (2-3), adult siblings (1) or other adult family members of client group participants (1-2)	

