team identifies individuals who are representative of consumers/customers at multiple levels within the organization who can inform the questions. These are our focus group participants – administrators, clinicians (nurses, case managers, physicians), clients and caregivers. Interviews and focus groups are conversational and discovery-oriented, with the goal of testing hypotheses. Focus group composition will be monitored to balance groups with respect to age, race and gender, taking care to include outlier perspectives. Once facts about the hypotheses have been obtained, the team will review all interview and focus group data, looking for emergent themes. This allows the team to determine the “value proposition” for the customer or key stakeholder, identifying potential “pain” and “gain” areas. The team can then determine actions needed to change or adapt iOTA to best fit the CMHC environment.

**Focus Group Makeup, Preparation & Topics** Purposive sampling methods will be applied to avoid bias in focus group responses, working with community partners to ensure group composition represents a broad range of perspectives. Six focus groups will be conducted at each community site, and will consist of:

- 1) Administrators (medical director, director of nursing, director of clinical services, case manager supervisor, clinic manager)
- 2) Prescribers (psychiatrists, advance practice nurses, physician assistants, primary care physicians)
- 3) Nursing staff (nursing staff, nurse care managers, nurse health coaches)
- 4) Community clinicians (community support specialists and case managers)
- 5) Transition-age clients (18-45 years)
- 6) Client family or caregiver (parents, adult siblings or other adult family members)

Once focus group participants are identified, they will be asked to participate in one in-person or phone visit to set up health goals and related text messages. They will then participate in 1-2 weeks of iOTA text messaging so as to facilitate optimal feedback on intervention adaptations. Focus groups will be scheduled within 1 week of completing the 2-week iOTA trial. Groups will be conducted at the CMHC site during a time that is convenient for participants, and will be facilitated by a research assistant facilitator and CMHC staff member taking additional notes. Groups will be digitally recorded. Focus group areas of interest will include:

- 1) What should the qualities and characteristics of the health coach/interventionist be?

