***Study Participants*** Aim 3 will include a randomized 24-week pilot study of the adapted intervention, followed by 12 weeks of text messaging intervention alone in 60 participants (30 at each study site). Participants will be CMHC clients aged 18-45 with eSMI receiving mental health services at each clinical site, and will be randomized 2:1, iOTA-eSMI intervention: health education control. Groups will be balanced to reflect the age, gender, racial and ethnic distribution of the client-base at each site. Targeted group size for this pilot study will permit exploration of treatment group interactions with age and with racial/ethnic differences. The study manager, under the supervision of the study statistician, will maintain control of the randomization matrix to ensure unbiased group assignment during the randomization process. Although this is not a blinded study, the PI's and health coaches will not be involved in any part of the randomization to further ensure an unbiased process.

***Inclusion criteria:*** i) aged 18-45 years, ii) "at-risk" weight defined as  $>7\%$  weight gain in the prior 2 years, overweight (BMI 25-29.9) OR class I obesity (BMI 30-32.49) iii) SMI diagnosis with  $<5$  years treatment,

iv) receiving case management services in one of the two CMHC study sites v) University of California, San Diego Brief Assessment of Capacity to Consent (UBACC) score  $> 14$  vi) not taking weight loss medications or participating in another behavioral weight loss intervention, vii) mild to moderate psychiatric symptom severity as measured by the Clinical Global Impression – Severity scale viii) willing and able to provide written informed consent.

**Exclusion criteria:** i) taking weight loss medications or participating in another behavioral weight loss intervention, ii) documented diagnosis of diabetes and/or treatment with an antidiabetes agent (diagnoses of hypertension and hyperlipidemia acceptable), iii) UBACC score  $\leq 14$ , iv) acute suicidality at time of screening, v) unwilling or unable to provide written informed consent.

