### **Participant Withdrawal:**

- Participants may withdraw at any point during or after the completion of the study with no penalty by contacting the study team.
- Investigators may choose to withdraw a participant from the study if it is unsafe to continue participation.
- If a subject withdraws from the study, the research team may only use and share information already collected for the study. Subject information may still be used and shared as necessary to maintain the integrity of the research, for example, to account for a participant's withdrawal from the research study or for safety reasons.

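### Parts of the safety text do not describe this trial, and tolerability, part of the primary goal, has no designated measure or adverse-event summary

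*Protocol*

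**What the plan says.** **Who is in the trial.** The Aim 1 exclusion criteria read "not willing/able to provide written informed consent; ii) participants under age 18". Table 1 fills the caregiver groups with "Parents (2-3), adult siblings (1) or other adult family members of client group participants (1-2". Under Aim 3, Study Participants, the randomised phase is "followed by 12 weeks of text messaging intervention alone in 60 participants (30 at each study site"; the age range is 18 to 45, and the inclusion criteria refer to two CMHC study sites.

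**What the safety and risk text says.**
- Relationship: "Child subjects will include only those with a variant in a suspected brain gene". It adds the custody requirement and describes participants as drawn from Intellectual Disabilities Research Centers.
- Severity: the same text as Definitions of Adverse Events.
- Safety and Compliance Monitoring: concerns are "communicated promptly to the 3 lead sites and handled accordingly". Of the DSMB it says "These members are expertise in areas of administrative data and child welfare reporting, both key issues pertinent to study implementation".
- Reporting Procedures: 13 sites.
- Potential Risks: a bullet on a breach of genetic data.
- Expectedness and Data Collection Procedures for Adverse Events: both print one sentence saying the study may be discontinued if outcome data show harm to caregivers and families. The randomised participants are not named.

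**Tolerability.** Aim 3 lists it among the things the pilot will assess. The rationale for the 24-week length makes it part of the primary goal, and the SAP repeats it as a goal of the funding mechanism. The outcomes named in Data Analysis/Statistical Considerations and in the SAP are weight, BMI, psychophysical skills and self-efficacy, plus exploratory measures of feasibility, engagement and implementation.

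**The concern.** A safety section should let a PI classify an event, route it, and know whose harm would prompt discontinuation. Here the two sections whose headings promise causality and severity rules contain neither, and one of them sets eligibility conditions that conflict with the trial's own criteria. Read literally, the custody condition bears on the adult siblings whom Table 1 invites. The program-officer routes turn on seriousness and relatedness, which this text does not define.

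The tolerability gap is a separate matter. A trial run exactly to plan could finish without a labelled tolerability result to carry into the planned R01 application, although tolerability is a stated goal. The arms also differ in contact between visits: daily goal texts and phone check-ins as needed on iOTA, one weekly health tip on control. A log fed only by what happens to reach staff could therefore fill unequally by arm.

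**Working it through.** **1. Site count.** Inputs from Aim 3, Study Participants: 60 in total, 30 per site. Sites = 60/30 = 2, which agrees with the two CMHC study sites in the inclusion criteria. The 13 in Reporting Procedures does not reproduce: 13 × 30 = 390 participants, or 60/13 = 4.6 per site.

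**2. Safety text against the design.**

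| Safety or risk text | Design text | Compatible? |
|---|---|---|
| Children with a gene variant (Relationship) | Under-18s excluded in Aim 1; Aim 3 aged 18 to 45 | No |
| Caregivers need permanent custody (Relationship) | Adult siblings in caregiver groups (Table 1) | No |
| 13 sites (Reporting Procedures) | Two CMHC sites of 30 | No |
| DSMB expertise in child welfare | Adults with early SMI | Does not fit |
| Genetic data (Potential Risks) | No procedure collects any | Does not fit |
| Severity | Repeats all 101 words of Definitions of Adverse Events | No grading given |
| Discontinuation for harm to caregivers and families | Caregivers do receive texts in Aim 1: "They will then participate in 1-2 weeks of iOTA text messaging" | Incomplete: randomised participants not named |

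**3. Program-officer routes in Reporting Procedures.** Cross serious, expected and related, each yes or no: 2 × 2 × 2 = 8 event types.
- 10-business-day notice (serious and unexpected): 2 types.
- Annual summary (expected, or not related): 4 + 4 − 2 = 6 types.
- Both routes (serious, unexpected, not related): 1 type, which is no conflict.
- Covered: 2 + 6 − 1 = 7. Left over: 8 − 7 = 1, the non-serious, unexpected, related event.

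All 8 types go to the IRB within 24 hours, a step that needs no classification.

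**4. Is tolerability measured?** The participant battery and medication log list 9 items for each visit and the health-coach list 4, so 13. The feasibility, appropriateness and acceptability questionnaire makes 14, because its text says every coaching visit (its heading says midpoint and endpoint). None of the 14 is an adverse-event question. Neither analysis section designates a tolerability measure or an adverse-event table. The annual funder summary in Reporting Procedures is administrative, is not described as by arm, and covers only expected or unrelated events.

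**5. What a by-arm table could show.** With full recruitment, 2:1 allocation gives 60 × 2/3 = 40 and 60/3 = 20.
- Zero events of a type, one-sided 95% upper bound 1 − 0.05^(1/n): 7.2% for n = 40 and 13.9% for n = 20.
- Chance of at least one event, 1 − (1 − p)^n. The documents give no event rates, so p is assumed. At 1%: 33% and 18%. At 5%: 87% and 64%. At 10%: 98.5% and 87.8%.

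**The case against.** The strongest reply is that the misfitting text has little practical force. Operative eligibility sits under the inclusion and exclusion headings. No one under 18 is enrolled, so the child rule applies to nobody, and only the custody clause could bite. That limits the harm but does not remove the contradiction, and the 13-site sentence is attached to a reporting duty.

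Several stronger readings are tempting, and the documents do not support them.
- *Randomised participants are unprotected.* A reader might infer this from the discontinuation sentence. The IRB can halt the protocol, a DSMB is described, and "Investigators may choose to withdraw a participant from the study if it is unsafe to continue participation".
- *One event type never reaches a program officer.* Only a written route in Reporting Procedures is missing. Medical Monitoring places a program officer at the monthly PI meetings, and the University and NICHD guidelines it cites may supply the missing definitions.
- *Adverse events are merely logged.* The data-collection section also states monthly safety monitoring and immediate IRB contact. What is missing is a question put to participants.
- *Tolerability is ignored.* Retention and acceptability are analysed, including their impact on effectiveness, and satisfaction surveys are sought from dropouts. They bear on tolerability but are not designated as measures of it.
- *Three rival site counts and two rival monitoring frequencies.* Lead sites need not be enrolling sites, and weekly teleconferences can coexist with monthly meetings. Only 13 is clearly irreconcilable.

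It is also fair to say that the SAP places statistical testing of effects outside the pilot's scope. A descriptive summary respects that.

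**Conclusion.** The point has two parts of different weight, and it should be fixed.

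**Wrong as written.** The Relationship text, the 13-site figure, the DSMB-expertise sentence and the genetic-data bullet do not describe this trial. Severity has no grading, Relationship has no relatedness rule, and the discontinuation sentence is incomplete. On routing, one of eight event types has no written program-officer route in Reporting Procedures; IRB reporting is intact for all eight. This rests on the current protocol text alone and assumes that the cited guidelines are not meant to override it.

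**A cheap improvement.** A component of the primary goal has no designated measure, no adverse-event summary and no adverse-event question among the 14 each-visit items. Any by-arm result would be imprecise at about 40 versus 20, assuming full recruitment.

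A reader might infer that the weight comparison or the sample size is compromised. Neither depends on any of this text.

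**What to change.** **Protocol.**
- Keep the adverse-event log, the 24-hour IRB report and the 10-business-day SAE notice.
- Remove or replace the Relationship and Severity text, the DSMB-expertise sentence, the 13-site figure and the genetic-data bullet.
- Check Post-study Adverse Event (its reference to the family) and Participant Enrollment (probands) for the same carry-over.
- Reconcile the discontinuation sentence with the Aim 3 population. Reconcile Medical Monitoring, whose independent-board heading is followed by PI monitoring, with the DSMB in Safety and Compliance Monitoring.
- Define seriousness and relatedness, or cite the guideline that does, and state the program-officer route for the one uncovered event type.
- Minor: clarify the three lead sites, weekly versus monthly PI monitoring, and which program office is meant.

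**Data collection.** Ask the same adverse-event questions at the existing monthly visits in both arms.

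**SAP.** Add a descriptive by-arm tolerability summary, without testing: AEs, SAEs, withdrawals and retention. Change in scales already collected, such as the PHQ-9, CGI and loss-of-control eating scale, could be added as an option.

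**Cost.** One protocol amendment, one SAP paragraph and a few minutes per visit. No new scale or visit is needed.
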